9.1.4. Statistical Analysis for Pharmacokinetics

The parameters for 765IGF-MTX, 765IGF, methotrexate, and 7-OH methotrexate will be expressed by descriptive statistics (geometric mean, median, standard deviation and coefficient of variation). The primary pharmacokinetic parameters investigated for each compound will be AUC_{0-t} , $AUC_{0-\infty}$, C_{max} and λ_z . Descriptive statistics will be calculated for the demographic data. Graphs and correlations will be used to examine the distribution of values and bivariate relationships.

9.2. Pharmacodynamic Assessment

Pharmacodynamic samples will be assessed on D1 of cycle 1, D1 and D15 of cycle 2, and D15 of cycles 4 and 6.

Systemic responses are defined as serum concentration of IGF-1 and plasma and whole blood concentrations of IGF-1R, which will be measured for all subjects and used to assess whether 765IGF-MTX has affected the production of these biological markers. Measures of toxicity (e.g., changes WBC counts, differential cell populations, platelets, etc.) are also considered systemic PD variables.

Pharmacodynamic data will be fit to an appropriate model, using maximum likelihood estimation. To determine whether any relationship exists between systemic activity of drug and biomarkers, the individual baseline corrected maximum biomarker concentrations will be plotted against individual 765IGF-MTX pharmacokinetic values, and Pearson's correlation coefficients will be calculated.

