[name]
 Mayo Clinic
 Division of Hematology
 Dept. of Internal Medicine
 [name]
 [name]
 [contact]
 [contact]
 [contact]

IND Sponsor Contact Information:

[name].,
 IGF Oncology,
 [name],
 [name]
 [contact]
 [contact]

Synopsis

Primary Objective:

The primary objective of this study is to determine the safety and tolerability of utilizing the insulin-like growth factor-1-methotrexate conjugate, 765IGF-MTX for the treatment of advanced, previously treated myelodysplastic syndrome (MDS), chronic myelomonocytic leukemia (CMML) and oligoblastic acute myelogenous leukemia (oligoblastic AML or O-AML), including determining the maximum tolerated dose (MTD).

Secondary Objective:

The secondary objective of this study is to determine the clinical benefit of 765IGF-MTX as measured by partial and complete remission rates, relapse-free survival, and overall survival in patients with advanced, previously treated MDS, CMML, or O-AML.

Patient Population:

[figure not shown]
- Diagnosis of MDS, CMML or O-AML that is refractory to or intolerant of standard therapy and is no longer likely to respond to such therapy
- Patient must have recovered from the acute toxic effects (\leq grade 1 CTCAE v.4.0) of previous anti-cancer treatment prior to study enrollment
- Age 18 years or older
- ECOG performance status 0, 1, or 2 (appendix III)

Study Design:

This pilot study will evaluate use of IGF-Methotrexate conjugate (765IGF-MTX) in patients with advanced, previously treated MDS, CMML and O-AML. 765IGF-MTX at a dose of 0.20 to 2.5 μ equivalents per kg is administered as an IV infusion over 1.5 hours on days 1, 8 and 15 of a 28 day cycle. Treatment continues until disease progression, as assessed after 2 cycles, unacceptable toxicity, or patient refusal. Assessment of response will be confirmed by bone marrow studies performed at the end of cycles 2, 4, and 6 (each +/- 3 days).

Once a final maximum tolerated dose level (MTD) is determined, the pharmacokinetics (PK) of 765IGF-MTX will be assessed on days 1 and 2 and days 15 and 16 of cycle 1 at the MTD in three patients.

Study Schema

Pharmacodynamic samples on day 1 of cycle 1, days 1 and 15 of cycle 2, and day 15 of cycles 4 and 6 before 765IGF-MTX administration.

At the MTD: Pharmacokinetic samples starting on day 1 (including time points on day 2), and day 15 (including time points on day 16) of cycle 1

Dose Finding Component: 1 cycle = 28 days

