- Maximum Tolerated Dose (MTD) Cohort with pharmacokinetics (PKs) and pharmacodynamics (PD): The MTD will be defined as the highest dose associated with DLT in less than 33% of patients treated. Once the MTD is determined, enrollment will continue until 9 patients total are accrued at the MTD. For this group, pharmacokinetics will be performed on at least 3 patients before and for up to 48 hours after drug administration on days 1 and 15 of cycle 1. Pharmacodynamic samples will be assessed on day 1 of cycle 1, and days 1 and 15 of cycle 2 before the infusion of 756IGF-MTX, and one sample will also be drawn within the fourth week of each treatment cycle.

If none of the dose levels are acceptable at study completion, an optimal dose level will not be identified and the drug does not warrant further investigation.

Dose limiting toxicity (DLT) for a patient is defined as one of the following events occurring during cycle 1:

- Grade 4 or greater treatment related hematologic toxicity for > 7 days during the first cycle (28 days) of therapy
- Grade 3 or greater treatment related clinical non-hematological toxicity (excluding \geq grade 3 nausea, vomiting, or diarrhea without maximal medical intervention and/or prophylaxis) during the first cycle (28 days) of therapy
- Febrile neutropenia during the first cycle (28 days) of therapy

- Platelets less than $10 \times 10^9/L$ with clinically significant bleeding during the first cycle (28 days) of therapy

Additional patient cohorts will not be enrolled until 1 of 1 (with no grade 2 toxicity), 3 of 3, 5 of 6, or 7 of 9 patients at the current dose level complete all planned treatment for cycle 1 (defined as 3 doses of 765IGF-MTX without DLT and are able to start cycle 2 with no more than a 2 week delay).

The MTD will be defined as a dose level at which fewer than 33% of patients treated experience a DLT.

A minimum of 9 patients are to be treated at the MTD to assure safety and 765IGF-MTX based pharmacokinetics will be performed on at least 3 patients in total.

Pharmacokinetics will be performed before and for up to 24 hours after drug administration on days 1 (for 24 hrs) and 15 (for 24 hrs) of cycle 1. Pharmacodynamic samples will be assessed pre-dosing on day 1 of cycle 1, pre-dosing on days 1 and 15 of cycle 2, and pre-dosing on day 15 of cycles 4 and 6.

5. Selection of Patients

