8.2. Research Related Procedures

	Baseline (within 28 days of Cycle 1, D1)	C1D1	C1 D15	C2 D1	C2 D15	Every 8 weeks (± 1 week) up to week 24	Cycles 4 and 6, D15
PKs per section 9.1		x ¹	x ¹				
ECG (QT study) done during PK blood collection per section 9.3. PK patients only. ²		x ²	x ²				
Serum IGF-1 level. All subjects.		x ³		x ³	x ³		
Plasma and whole blood IGF-1R level. All subjects.		x ³		x ³	x ³		x ³
Anti-765IGF antibody assay. All subjects.		x ³		x ³	x ³		x ³
Neutralizing antibodies. All subjects.		x ³		x ³	x ³		x ³
IGF-1R expression in bone marrow biopsy and aspirate by IHC and flow cytometry. All subjects.	x ⁴					x ⁴	
IGF-1R expression in blood cells by flow cytometry. All subjects.	x ⁵					x ⁵	

¹ Done only in the PK patients in the MTD. Pre-765IGF-MTX infusion (at the time of am labs if am labs are within one hour of 765IGF-MTX infusion), 5 min before the infusion ends (+/- 5 minutes), and at the following time points after completion of the infusion: 30 min (+/- 5 minutes), 60 min (+/- 15 minutes), 2 h (+/- 15 minutes), 4 h (+/- 15 minutes), 6 h (+/- 15 minutes), 8 h (+/- 15 minutes and 24 h (+/- 2 hours)). The 8 hour time point will be collected on day 1 but not on day 15.

² Done only in PK patients in the MTD. Pre-765IGF-MTX infusion (+/- 5 minutes), and 30 min (+/- 5 minutes) after starting the infusion, at the following time points after completion of the infusion: 60 min (+/- 15 minutes) and 3 hours (+/- 15 minutes). In all patients, ECG is done at baseline, on day 1, cycle 1 (before the infusion), and 30 days (± 1 week) after the final dose (see section 8.1).

³ Blood draw prior to infusion

⁴ Bone marrow biopsy and aspirate will be collected at baseline and every 8 weeks (± 1 week) up to week 24, i.e., after cycles 2, 4, and 6, before the first dose of the next cycle. If no bone marrow aspirate viably frozen for flow cytometry is available from a patient in the 28-day baseline period before cycle 1, day 1, the patient may still enroll and no new bone marrow biopsy will be required for a baseline sample.

⁵ Whole blood collection in EDTA tubes.

9. Correlative Studies

Information on the collection of blood samples for the correlative studies (collection tubes to be used, volume of blood drawn, collection processing, aliquot procedure and storage, and particular assay to be used) can be found in a laboratory manual to be supplied.

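### The exposure-biomarker correlation in section 9.2 rests on three to nine PK patients at one dose level, too few to show or exclude a moderate relation, and no dose-biomarker analysis in all patients is named

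*Combined protocol and SAP*

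**What the plan says.** Section 9.2 states its aim as a question of existence: "To determine whether any relationship exists between systemic activity of drug and biomarkers". The method is that each patient's highest marker value, corrected for baseline, is plotted against that patient's PK values, and "Pearson's correlation coefficients will be calculated". Only patients with PK samples can enter that analysis.

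The synopsis places PK on two occasions "of cycle 1 at the MTD in three patients". Section 4 gives a minimum instead: "pharmacokinetics will be performed on at least 3 patients in total". Footnote 1 to the section 8.2 schedule limits the sampling: "Done only in the PK patients in the MTD". Section 4 continues enrolment until nine patients are accrued at the MTD.

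The markers are collected more widely. The section 8.2 schedule lists "Plasma and whole blood IGF-1R level. All subjects", and does the same for serum IGF-1. Both are drawn before infusion on cycle 1 day 1, cycle 2 day 1 and cycle 2 day 15, with later IGF-1R samples. The dose table has up to five levels, from 0.20 to 2.5 µeq/kg.

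Section 13.2 promises summaries by dose level and overall. Section 13.2.1 uses the assigned Cycle 1 dose level as covariate for remission, overall survival and progression-free survival. Sections 13.5.2, 13.5.4 and 13.5.5 relate markers to response or toxicity. None of these names a dose-biomarker analysis.

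**The concern.** A Pearson coefficient from three points has one degree of freedom. It is often large when nothing is there, and it seldom passes a conventional threshold when something is. Restricting PK to one dose level also means that exposure varies only between patients, which narrows the range over which a relation could appear.

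At stake is the reading of one exploratory objective. A coefficient of 0.8 or 0.9 could be taken as evidence that the drug acts on the IGF axis, and a small one as evidence that it does not. Neither reading would be justified. Meanwhile the trial collects the same markers in every patient, over a planned dose range of up to 2.5/0.20 = 12.5-fold, without naming an analysis that links the two.

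**Working it through.** The plan gives no power or precision figure for this correlation, so there is nothing to reproduce.

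**Inputs from the documents.** PK patients: three (synopsis), or at least three (section 4). I take nine, the planned MTD cohort, as the upper end. One sentence in section 4 calls nine a minimum, but PK starts only once the MTD is determined, so patients already treated at that level would not contribute. PK dose levels: one.

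**Assumptions.** Bivariate normal data and a two-sided 5% level. Section 9.2 sets no level; 5% serves only as a yardstick.

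**Chance of a large coefficient with no relation.** Under no relation, t = r·√(n−2)/√(1−r²) has n−2 degrees of freedom. For n = 3:
- r = 0.8 gives t = 0.8/0.6 = 1.333, and P(|t₁| > 1.333) = 1 − (2/π)·arctan(1.333) = 0.410.
- r = 0.9 gives t = 0.9/0.436 = 2.065, and the probability is 0.287.

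**Critical value.** |r| = t/√(n−2+t²).
- n = 3: 12.706/√(1 + 161.45) = 0.997.
- n = 9: 2.365/√(7 + 5.59) = 0.666.

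**Interval at an observed r of 0.** By Fisher's z this is ±tanh(1.96/√(n−3)). It does not exist at n = 3. At n = 9 it is ±tanh(0.800) = ±0.66.

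**Power**, by simulation:

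| PK patients | P(|r| > 0.8), no relation | Critical |r| | Power, true r = 0.5 | Power, true r = 0.7 | Power, true r = 0.8 |
|---|---|---|---|---|---|
| 3 | 41% | 0.997 | 7% | 9% | 11% |
| 4 | 20% | 0.950 | 9% | 17% | 25% |
| 6 | 5.6% | 0.811 | 17% | 37% | 56% |
| 9 | 1.0% | 0.666 | 29% | 62% | 82% |

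For 80% power, ((1.960 + 0.842)/arctanh ρ)² + 3 gives 30, 14 and 10 patients for a true r of 0.5, 0.7 and 0.8.

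**What using dose in all patients would add.** This depends on the layout, which is not fixed (section 13.1). I assumed a slope on log dose that gives a correlation of 0.6 over five equally filled levels, then changed only the layout:
- 1, 1, 1, 1, 9 patients at levels 1 to 5: power 59%.
- 1, 1, 9, 3 patients at levels 1 to 4: power 32%.
- 1, 9, 3 patients at levels 1 to 3: power 17%.

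In the first layout the mean log dose is 0.459 and the sum of squares is 8.52. The single patient at 0.20 µeq/kg contributes (−1.609 − 0.459)² = 4.28, or 50% of it. The two lowest-dose patients together contribute 72%.

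**The case against.** **Three is a floor.** This stands. If all nine MTD patients gave PK, a correlation near 0.8 could be detected with 82% power. A reader might infer from the three-patient figures that the correlation is pure noise whatever happens. The documents do not support that, because section 4 allows more than three. But nothing commits the trial to more than three, and even nine leaves a moderate relation unresolved.

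**The all-subject data are already used.** A reader might infer that the plan leaves these data unused. It does not. Section 9.2 says that the markers from all subjects will be used to judge whether the drug has affected their production, and that pharmacodynamic data will be fitted by maximum likelihood. Section 13.2 summarises by dose level, and section 13.5.2 adds graphs and correlations. What remains is that the model has no named covariate or population, and none of these passages specifies a dose-biomarker analysis.

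**No test is planned, and detail is deferred.** Section 9.2 sets no significance level, and section 13 calls itself an overview, with a full SAP to follow before database lock. Both are fair. The power figures show how little the coefficient can tell; they do not describe a failed test. Deferral makes the change easy but does not alter the method that section 9.2 already names.

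**Dose is not AUC.** This also stands. A reader might assume a correlation of 0.6 for dose and 13 to 30 patients, and claim power of roughly 63% to 96%. That figure is not supportable. A dose-biomarker correlation is a different quantity from a PK-biomarker correlation, all five levels may not open, and some patients will have no post-baseline sample.

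**Conclusion.** The point holds as a cheap improvement to an exploratory analysis. As specified, the correlation uses three to nine patients at one dose level. At three, a coefficient above 0.8 arises by chance 41% of the time. At nine, a true correlation of 0.5 is detected about 29% of the time, and an observed zero is compatible with anything from −0.66 to 0.66. The stated aim of determining whether a relation exists cannot be met for a moderate relation.

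The figures assume normal data and a two-sided 5% yardstick. Under the section 8.2 schedule, PK patients who stop before cycle 2 have no post-baseline marker value, so the usable number may be smaller still.

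An analysis on dose would draw on more patients and a wider exposure range. Its gain over the PK correlation cannot be stated as a number, because the levels opened and the patients at each are unknown. The primary objective is untouched.

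**What to change.** In the full SAP, prespecify as the main exposure-biomarker analysis a regression or rank correlation, with 95% CI, of log change in each marker from baseline to the cycle 2 samples on log assigned Cycle 1 dose level. Include every patient with a post-baseline sample.

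Use the per-infusion dose level, not cumulative dose. Cumulative dose grows with time on treatment, which ends at progression or toxicity, so it would mix exposure with disease course. The assigned Cycle 1 level is already the covariate in section 13.2.1. Intra-patient escalation is allowed only after two cycles, so the cycle 2 samples come before it.

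Keep the section 9.2 plot, with PK patients as individual points, and report no PK correlation coefficient when only about three patients have PK. Show the dose-biomarker data by patient, and report how far the estimate depends on the lowest-dose patients.

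The cost is SAP wording and one extra analysis, with no new samples. The downsides are that dose is a cruder measure than AUC, patients who stop before cycle 2 do not contribute, and a few low-dose patients may be highly influential.

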9.3. Evaluation of potential of 765IGF-MTX for QT prolongation

QT evaluation will be performed in the PK subjects only during PK collection times by ECG immediately prior to the 765IGF-MTX infusion, 30 minutes after starting the infusion, and at the following time points after completion of the infusion: 60 minutes and 3 hours. In all subjects, QT evaluation will be performed by ECG at baseline (within 14 days of enrollment), at cycle 1 day 1 (before the infusion) and at 30 days (± 1 week) after the final dose of 765IGF-MTX.

9.4. Serum IGF-1 Level and 765IGF-MTX Toxicity/Response

Blood serum samples from before the infusion on D1 of cycle 1, and before the infusion on D1 and D15 of cycle 2 will be collected from each patient to determine if pre- and during treatment serum soluble IGF-1 level is associated with 765IGF-MTX toxicity and/or response. Quantification of IGF-1 in serum will be performed by Q2 Solutions, using Chemiluminescence methodology. A descriptive analysis will be done between clinical response and marker levels. Please see the laboratory manual for biomarker collection procedures.

9.5. Plasma and whole blood IGF-1R Level and 765IGF-MTX Toxicity/Response

Plasma and whole blood samples from before the infusion on D1 of cycle 1, and before the infusion on D1 and D15 of cycle 2 and on D15 of cycles 4 and 6 will be collected from each patient to determine if pre- and within-treatment serum and blood IGF-1R level is associated with 765IGF-MTX toxicity and/or response. Quantification of IGF-1R in plasma will be performed by IGF Oncology using western blotting. A descriptive analysis will be done between clinical response and marker levels. Please see the laboratory manual for biomarker collection procedures.

9.6. Formation of anti-765IGF-MTX antibodies.

Serum samples from before the infusion on D1 of cycle 1, and before the infusion on D1 and D15 of cycle 2 will be collected from each patient and analyzed for anti-drug antibodies by an assay the sponsor has used for detecting anti-765IGF-MTX antibodies in preclinical tests in dogs and rats. The assay is a sandwich ELISA involving plating serum in 96-well plates, adding drug to the wells of the plates to bind to any anti-drug antibodies that may be present in the serum, and then detecting bound 765IGF-MTX drug with an anti-IGF-HRP conjugate antibody from R&D Systems, Quantikine human IGF-1 ELISA kit.

That sandwich assay detects antibodies against 765IGF-MTX.

The serum samples will also be analyzed for the presence of neutralizing antibodies. In this assay, serum will be mixed with 765IGF-MTX in an in vitro assay for killing of human MCF7 breast cancer cells to determine whether the addition of patient serum affects the minimum inhibitory concentration of 765IGF-MTX in inhibiting growth of MCF7 cells. This assay will be performed on the same serum samples collected before treatment on Cycle 2, days 1 and 15 and on day 15 of cycles 4 and 6. Please see the laboratory manual for biomarker collection procedures.

Risk assessment. The risk to patients from assaying for anti-765IGF-MTX antibodies is minimal and arises only from an additional blood draw before the infusion on D1 of cycle 1, and D1 and D15 of cycle 2. A small amount of blood (7.5 mL/draw) will be taken, which will have no effects on patient health. The risk to patients from possibly developing anti-765IGF-MTX antibodies is also small and would be lessened by our knowledge as to whether they are developing these antibodies. First, none of the dogs and none of the rats developed anti-drug antibodies in preclinical testing, so it appears unlikely that patients will develop anti-765IGF-MTX antibodies. The risk to patients from developing the antibodies, if it occurs, would be that the antibodies would be expected to possibly reduce the effectiveness of the drug, and would raise a risk of an anaphylactic reaction to administration of the drug. Anaphylactic reactions occur with some biologic medicines, such as Rituximab, and can usually be managed with antihistamines, such as diphenhydramine. Formation of antibodies against 765IGF-MTX may also potentially cause similar side effects of antibodies against IGF1 receptor, such as the possibility of development of hyperglycemia. Monitoring blood sugar levels will be routinely performed in this study.

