CTCAE Grade 1 Allergic Reaction/Hypersensitivity: (Transient flushing or rash, drug fever $< 38^{\circ}C$): Supervise without further treatment for allergic reaction/hypersensitivity.

CTCAE Grade 2 Allergic Reaction/Hypersensitivity: (Rash, flushing, dyspnea, urticaria, drug fever greater than or equal to $38^{\circ}C$) and/or asymptomatic bronchospasm: Interrupt the infusion. If symptoms abate, attempt re-infusion at a slower rate. If the symptoms recur,

discontinue infusion and follow for recurrent allergic reaction/hypersensitivity in the next paragraph.

Recurrent CTCAE Grade 2 or CTCAE Grade 3 or 4 Allergic Reaction/Hypersensitivity:

Stop the infusion. Administer additional doses of H1 and H2 blockers intravenously. Administer IV steroids and consider epinephrine and bronchodilators as clinically indicated.

CTCAE Grade 3 or 4 Allergic Reaction/Hypersensitivity: Stop the infusion. Administer additional doses of H1 and H2 blockers intravenously. Administer IV steroids and consider epinephrine and bronchodilators as clinically indicated. Will be permanently discontinued from study treatment.

Prior to re-challenge of Grade 2 allergic reaction/HSR and with all subsequent cycles:

The following prophylactic premedications are recommended for future infusions: give both an H1 and H2 blocker intravenously plus dexamethasone 20 mg (orally or intravenously) within 30 to 60 minutes before 765IGF-MTX infusion. Dexamethasone could be used at the investigator's discretion in subsequent cycles for recurrent (i.e. occurring despite slowing infusion as discussed above) Grade 2 reactions but would not be mandated.

An appropriate resuscitation plan should be in place and a physician readily available during the period of drug administration. If treatment delay necessitates a period longer than 4 weeks, treatment is stopped and the subject is discontinued from the study.

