9.7. Neutralizing antibodies and 765IGF-MTX Toxicity/Response

Serum samples from before the infusion on D1 of cycle 1 and before the infusion on D1 and D15 of cycle 2, and on D15 of cycles 4 and 6 will be analyzed for the presence of neutralizing antibodies. In this assay, serum will be mixed with 765IGF-MTX in an in vitro assay for killing of human MCF7 breast cancer cells to determine whether the addition of patient serum affects the minimum inhibitory concentration of 765IGF-MTX in inhibiting

growth of MCF7 cells. Please see the laboratory manual for biomarker collection procedures.

A descriptive analysis will be done correlating neutralizing antibody presence or levels with clinical response to, and toxicity of, 765IGF-MTX.

9.8. IGF-1R expression level in diseased cells of bone marrow aspirate via IHC and flow cytometry

When bone marrow aspirates are collected from patients, a portion will be clotted, fixed, and paraffin embedded; and a second portion will be shipped fresh the same day to Charles River Laboratories (Reno, NV) for flow cytometry assay of IGF-1R and CD34. A pathology report will be prepared for the fixed sample. The fixed samples will be held at Mayo Clinic and shipped together at the end of the study with their pathology reports to Quest Diagnostics for IGF-1R expression level testing by IHC with their test code 19429X.

The fresh second portion of the bone marrow aspirate will be kept at room temperature and shipped on the day of collection in an insulated container at room temperature to Charles River, Inc. (Reno, NV), for testing of IGF-1R and CD34 expression by flow cytometry. This assay will be similar to that of He et al.²⁸

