13.5.6 Antibody formation against 765IGF-MTX: Serum samples from before infusion on D1 of cycle 1, and before infusion on D1 and D15 of cycle 2 and day 15 of cycles 4 and 6 will be collected and analyzed for anti-765IGF-MTX antibodies. A descriptive analysis will be done correlating anti-765IGF-MTX antibody presence or levels with clinical response and toxicity.

13.5.7 Neutralizing antibodies and 765IGF-MTX toxicity/response: Serum samples from before infusion on D1 of cycle 1 and before infusion on D1 and D15 of cycle 2 and D15 of cycles 4 and 6 will be collected for presence of neutralizing antibodies. A descriptive analysis will be done correlating presence or levels of neutralizing antibodies with clinical response and toxicity.

13.5.8 IGF-1R expression level in bone marrow biopsies via IHC and flow cytometry and IGF-1R expression level in blood cells by flow cytometry: IGF-1R expression at baseline will be performed on paraffin-embedded fixed bone marrow aspirates by Quest Diagnostics by IHC and IGF-1R expression at baseline will be performed on fresh viable bone marrow aspirates and fresh whole blood by Charles River, Inc. by flow cytometry. If sample sizes are small and heterogeneous, clinical responses will be reported by dose and disease (MDS, CMML, or O-AML) type

14 Conduct of the Study

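### Patients who stop permanently in cycle 1 have no antibody sample after dosing, so antibody results go missing in relation to toxicity

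*Combined protocol and SAP*

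**What the plan says.** Below, C1D8 means cycle 1 day 8, and so on.

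- **Anti-drug antibodies.** Section 9.6 specifies "Serum samples from before the infusion on D1 of cycle 1, and before the infusion on D1 and D15 of cycle 2". Table 8.2 (row "Anti-765IGF antibody assay. All subjects") and section 13.5.6 add day 15 of cycles 4 and 6.
- **Neutralizing antibodies.** Section 9.7 uses C1D1 serum plus samples taken "before the infusion on D1 and D15 of cycle 2, and on D15 of cycles 4 and 6 will be analyzed". Section 13.5.7 gives the same times.
- **Timing within the day.** The footnote to both antibody rows of table 8.2 reads "Blood draw prior to infusion". The C1D15 cell is empty in both rows, and the table has no final-visit column.
- **Final visit.** Section 7.11 sets it 30 days (± 1 week) after the last dose. Its column in table 8.1 includes CBC and CMP but no antibody assay.
- **Stopping rule.** Of grade 3 or 4 hypersensitivity, section 7.2.1 says "Will be permanently discontinued from study treatment".
- **Rationale.** The risk assessment in section 9.6 says that antibodies, if formed, "would raise a risk of an anaphylactic reaction to administration of the drug".
- **Analysis.** Section 13.5.6: "A descriptive analysis will be done correlating anti-765IGF-MTX antibody presence or levels with clinical response and toxicity". Section 13.5.7 plans the same for neutralizing antibodies.

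**The concern.** The protocol itself names anaphylaxis as a possible consequence of antibody formation and plans to describe antibodies against toxicity. The first sample that could show antibodies formed on treatment is tied to the start of cycle 2. A patient whose reaction ends treatment in cycle 1 never gets there. Whether an antibody result exists therefore depends partly on toxicity, the variable it is to be compared with. In a dose-finding study with 9 patients at the MTD, one or two such gaps can change what a descriptive table shows.

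**Working it through.** The documents give no sample size, power or event figure for this point, so there is no stated result to reproduce. The check is a count from the schedules, followed by arithmetic on stated assumptions.

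**1. Antibody samples by last dose received** (table 8.2; sections 9.6, 9.7, 13.5.6, 13.5.7)

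| Last dose | Pre-treatment sample (C1D1) | Samples after dosing |
|---|---|---|
| C1D1 | 1 | 0 |
| C1D8 | 1 | 0 |
| C1D15, cycle 2 not started | 1 | 0 |
| C2D1 | 1 | 1 (before the C2D1 infusion) |

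**2. Which cycle 1 reactions matter.** Section 9.1.3 treats the first dose as given before any anti-drug antibody could be present. On that premise, a C1D1 reaction cannot reflect antibodies induced by treatment, and the pre-dose sample covers any that already existed. The gap that matters for the toxicity question is therefore a grade 3 or 4 reaction on C1D8 or C1D15. Other permanent cycle 1 leavers are missing from the incidence count as well.

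**3. How many patients.** The documents give no cycle 1 stopping rate. Let p be the assumed proportion stopping in cycle 1 for any reason, among the 9 MTD patients of section 4. The expected number without a result is 9p, and the chance of at least one is 1 − (1 − p)^9.

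| Assumed p | Expected (9p) | Chance of at least one |
|---|---|---|
| 5% | 0.45 | 1 − 0.95^9 = 37% |
| 10% | 0.9 | 1 − 0.90^9 = 61% |
| 20% | 1.8 | 1 − 0.80^9 = 87% |
| 33% | 3.0 | 1 − 0.67^9 = 97% |

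Section 4 defines the MTD by DLT in fewer than 33% of patients. Since 2/9 = 22% meets this and 3/9 = 33.3% does not, 2 of 9 is the ceiling on DLTs at the MTD. It does not estimate missing antibody results, because section 7.2.1 lets other DLTs continue at a lower dose level.

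**4. Direction of the effect (assumed example).** Suppose 3 of 9 patients form antibodies and 2 stop on C1D15 after a reaction.

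- If both stoppers are positive, the true incidence is 3/9 = 33%. The sampled patients show 1/7 = 14%, with none of those reactions among them.
- If both stoppers are negative, the sampled patients show 3/7 = 43%.

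Understatement therefore requires that early leavers are more often positive.

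**5. When a final-visit sample would fall** (last dose day + 30, ± 7)

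| Last dose | Study day (window) |
|---|---|
| C1D1 | 31 (24–38) |
| C1D8 | 38 (31–45) |
| C1D15 | 45 (38–52) |

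C2D1 is nominally day 29. Under section 7.1.1 it can be day 28, or as late as day 57 with a four-week delay.

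**The case against.** **Another cycle 1 sample may exist.** For the MTD cohort, one sentence of section 4 adds a pharmacodynamic sample in the fourth week of every cycle. Section 13.5.2 counts both antibody measures as pharmacodynamic parameters. This stands as a conflict to be settled, but not as an answer. Section 3.3.3 defines pharmacodynamics without antibodies. The later paragraph of section 4, the synopsis, table 8.2 and section 9.2 omit the sample. It does not clearly apply to someone already off treatment.

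**Survivor selection is only partial.** A reader might infer that the analysis covers only patients who tolerated cycle 1. The documents do not support that. Section 7.2.1 offers a lower dose level as an alternative to stopping after febrile neutropenia, prolonged grade 4 hematologic toxicity and grade 3 non-hematologic toxicity. It also allows re-challenge after grade 2 hypersensitivity. Patients who react in cycle 2 have earlier samples.

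**Bias is not demonstrated.** This stands. Section 9.6 considers antibody formation unlikely, since no dog or rat developed antibodies. With no reactions left among the sampled patients, an association could not be estimated, which differs from showing none. Nor does the plan count unsampled patients as negative: section 13.2.1 says that missing values are in general not imputed.

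**Serum IGF-1 and soluble IGF-1R.** These share the schedule up to C2D15 (section 9.4: "Blood serum samples from before the infusion on D1 of cycle 1, and before the infusion on D1 and D15 of cycle 2"), so the point might seem to extend to them. Sections 9.4, 9.5, 13.5.4 and 13.5.5 concern levels before and during treatment. The baseline sample is scheduled for everyone, and a draw 30 days after the last dose would not supply a within-treatment level.

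**Conclusion.** The gap is real and limited to antibodies. As scheduled in table 8.2 and sections 9.6 and 9.7, every patient who stops permanently in cycle 1 has zero antibody samples after dosing. This includes every patient with grade 3 or 4 hypersensitivity in that cycle. Antibody incidence and any antibody–toxicity association may be understated, on the condition that early leavers are more often positive, which the documents neither state nor exclude. The 37% to 97% range rests entirely on the assumed stopping rates and counts leavers for any reason, not only reactors.

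A reader might take 2 of 9 (22%) as the expected loss; for DLTs at the MTD it is only a ceiling. This is a suggestion to consider: the objective is correlative, the analysis is descriptive, and neither DLT assessment nor MTD selection depends on it. The laboratory manual, cited for collection procedures, was not available to check.

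**What to change.** 1. In table 8.2 and sections 9.6, 9.7, 13.5.6 and 13.5.7, add one serum sample for anti-drug and neutralizing antibodies at the existing 30-day final visit for all treated patients. For cycle 1 stoppers it falls nominally on study day 31 to 45, close to or after the planned C2D1 draw. Those who do not attend remain missing.
2. In 13.5.6 and 13.5.7, show patients without a post-dose sample separately from antibody-negative patients.
3. Reconcile the fourth-week sample in section 4 with table 8.2 and section 9.2, and state whether it includes antibodies.

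The cost is a small amendment and, per patient, one extra 7.5 mL tube (the volume in section 9.6), one ELISA and one cell assay. CBC and CMP are already drawn at that visit, so no visit is added. A draw at the moment of a reaction is not proposed: the ELISA works by adding drug to serum and detecting what binds, so circulating drug may interfere.
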